5.2 Concomitant Medications Allowed for the Duration of the Study

Table 2

Drug	Restrictions
Prednisone	Stable dose for 4 weeks prior to Visit 1 (see tapering/escalation guidelines above under section 5.0)
IVIg	Stable regimen for 4 weeks prior to Visit 1
IV methylprednisolone (pulse therapy)	Stable regimen for 4 weeks prior to Visit 1
Methotrexate and other IS agents including azathioprine, mycophenolate mofetil, leflunomide, cyclophosphamide, tacrolimus or cyclosporine	Stable dose for 6 weeks prior to Visit 1
Statin agents: Lovastatin, Simvastatin, Pravastatin, Fluvastatin, Atorvastatin and Fibric acid derivatives: Fenofibrate (Lipidil™, Lipidil micro™, Tricor), Gemfibrozil (Lopid™), Benafibrate (Bezalip™), Clofibrate (Atromid-S)	Stable dose for 6 weeks prior to Visit 1
Colchicine	Stable dose for 6 weeks prior to Visit 1
Hydroxychloroquine	Stable dose for 6 weeks prior to Visit 1

*When possible, patients will take no more than 2 immunosuppressive agents, not including prednisone, IVIg, colchicine, hydroxychloroquine

5.3 Concomitant Medications Not Allowed for the Duration of the Study

Table 3

Drug	Restrictions
Biologic agents	Not allowed throughout study
Colchicine	Initiation of new therapy is not allowed after Visit 1 or throughout enrollment.

Fibric acid derivatives: Fenofibrate (Lipidil™, Lipidil micro™, Tricor), Gemfibrozil (Lopid™), Benafibrate (Bezalip™), Clofibrate (Atromid-S)	Initiation of new therapy is not allowed after Visit 1 or throughout enrollment
Statin agents: Lovastatin, Simvastatin, Pravastatin, Fluvastatin, Atorvastatin	Initiation of new therapy is not allowed after Visit 1 or throughout enrollment
Hydroxychloroquine	Initiation of new therapy is not allowed after Visit 1 or throughout enrollment.

IVIG and IV methylprednisolone use throughout the trial:

- These medications will be allowed during the trial.
- Patients must be on a stable regimen of 4 weeks prior to Visit 1.
- Dose of IVIG and dosing interval of both agents must remain stable.
- Suggested guidelines for IVIG: one (1) - two (2) grams / kg monthly
Suggested guidelines for IV methylprednisolone or equivalent 10 - 30 mg/kg: IV once weekly to IV once per month.

5.4 Other Restrictions

- A patient may continue with an exercise program that was initiated before the 4 week period prior to the screening visit, regardless of the components of the program (stretching, muscle building, etc.)
- A stretching program may be initiated during the 4 week period prior to the screening visit or during the study period as long as there is no muscle building component to the program.

6.0 STUDY MEDICATION

Study Treatment: Abatacept

Definition of Investigational Product: A pharmaceutical form of an active substance or placebo being tested or used as a reference in a clinical study, including products already with a marketing authorization but used or assembled (formulated or packaged) in a way

different from the authorized form, or used for an unauthorized indication, or when used to gain further information about the authorized form.

In this protocol, the investigational product is abatacept. Abatacept will be provided by BMS in 50 mg pre-filled syringes, 87.5 mg pre-filled syringes and 125 mg prefilled syringes.

6.1 Study Medication Description

Abatacept Injection, 125 mg/Syringe (125 mg/mL), is a sterile solution for SC administration, which contains approximately 125 mg abatacept, 171 mg sucrose, 8 mg Poloxamer 188, 0.29 mg monobasic sodium phosphate, monohydrate, and 0.84 mg dibasic sodium phosphate, anhydrous, in Water for Injection. The composition of this solution has a ratio of monobasic sodium phosphate, monohydrate, and dibasic sodium phosphate, anhydrous, used to achieve the target pH of 7.2.

Two presentations of Abatacept Injection 125 mg/Syringe are currently commercialized:

[figure not shown]
- Abatacept injection prefilled syringe with UltraSafe Passive Needle Guard (SSI NeedleGuard) and flange extenders
- Abatacept injection prefilled syringe with flange bags have been observed.

Abatacept injection, 50 mg/syringe (50 mg/ml) and Abatacept injection, 87.5 mg/syringe (87.5 mg/ml) will also be available for subjects with body weight <50 kg

6.2 Study Medication Schedule

At Visit 1 (week 0), eligible subjects will be instructed on the use and potential side effects of subcutaneous abatacept and will be started on the study drug (abatacept 125 mg SQ weekly for subjects with body weight ≥ 50 , or abatacept 87.5 mg SQ weekly for subjects with body weight < 50 kg). Subjects will be on weekly Abatacept for the duration of the study (from week 0 through week 24). For patients not improving with therapy by at least 5% on at least 3 of 6 core set measures at week 12 (visit 3), and rated as unchanged or worsened from visit 1 by the study physician, they would be offered the opportunity to increase their dose of treatment to abatacept 212.5 mg (125 mg prefilled syringe plus 87.5 mg prefilled syringe) weekly subcutaneously for subjects with body weight ≥ 50 kg or to abatacept 137.5 mg (87.5 mg prefilled syringe plus 50 mg prefilled syringe) for subjects with body weight < 50 kg, or to continue on their present dose.

STUDY SCHEMATIC

The short lines indicate phone follow-ups, which will occur at weeks 2, 4, 8, 10, 14, 16, 20 and 22

An open label extension phase will be offered for up to 6 months (visit could be in time less than that) for patients meeting the definition of improvement and who are rated by their study physician as at least minimally improved.

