Study SC-1 was a randomized, double-blind, double-dummy, non-inferiority study that compared the efficacy and safety of abatacept administered subcutaneously (SC) and intravenously (IV) in 1457 subjects with RA, receiving background methotrexate, and experiencing an inadequate response to methotrexate (MTX-IR). The safety experience and immunogenicity for abatacept administered subcutaneously was consistent with intravenous Studies I-VI. Due to the route of administration, injection site reactions and immunogenicity were evaluated in Study SC-1 and two other smaller studies discussed in the sections below. The highest dose tested in adults is 200 mg weekly.

Injection Site Reactions in Adult RA Patients Treated with Subcutaneous ABATACEPT

Study SC-1 compared the safety of abatacept including injection site reactions following subcutaneous or intravenous administration. The overall frequency of injection site reactions was 2.6% (19/736) and 2.5% (18/721) for the subcutaneous abatacept group and the intravenous abatacept group (subcutaneous placebo), respectively. All these injection site reactions (including hematoma, pruritus, and erythema) were mild (83%) to moderate (17%) in severity, and none necessitated drug discontinuation.

Immunogenicity in Adult RA Patients Treated with Subcutaneous abatacept : Study SC-1 compared the immunogenicity to abatacept following subcutaneous or intravenous administration. The overall immunogenicity frequency to abatacept was 1.1% (8/725) and 2.3% (16/710) for the subcutaneous and intravenous groups, respectively. The rate is consistent with previous experience, and there was no correlation of immunogenicity with effects on pharmacokinetics, safety, or efficacy.

Immunogenicity and Safety of Subcutaneous abatacept Administration as Monotherapy without an Intravenous Loading Dose:

Study SC-2 was conducted to determine the effect of monotherapy use of abatacept on immunogenicity following subcutaneous administration without an intravenous load in 100 RA patients, who had not previously received abatacept or other CTLA4Ig, who received either subcutaneous abatacept plus methotrexate (n=51) or subcutaneous abatacept monotherapy (n=49). No patients in either group developed anti-product antibodies after 4 months of treatment. The safety observed in this study was consistent with that observed in the other subcutaneous studies.

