Evaluation of Risk/Benefit Ratio: If abatacept proves to be effective, many such patients with JDM may ultimately benefit from this therapy. Such benefits may include improved symptoms and health. Practitioners may gain increased knowledge and treatment of myositis in clinical practice. Subjects participating in this study may experience some benefit during the period of study medication therapy. Evaluation is performed as per the statistical information provided in the protocol. The risks for those subjects involved in this study are reasonable when compared to the potential

disease damage and catastrophic sequelae that occurs in adult and pediatric patients with inflammatory myopathy.

Reproductive Risks: Animal studies to determine the effects of the study drug on the fetus have not been done. To avoid risk to the fetus, it is important that female participants or female partners of male participants take care to avoid becoming pregnant during this study. Avoiding sexual activity is the only certain method to prevent pregnancy. However, females of child-bearing potential must be willing to use an appropriate method of birth control (such as female use of a diaphragm, intrauterine device (IUD), or contraceptive sponge, in addition to male use of a condom) or the female should be using prescribed “birth control” pills, injections, or implants throughout the study. Even with use of these birth control measures, pregnancy could still result. The risks of receiving the study drug while pregnant include potential loss of pregnancy or possible birth defects. Females of child-bearing potential will undergo a urine pregnancy test prior to exposure to the study drug. In the pediatric group the parent signing the consent will be informed of the result of the pregnancy test.

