3.0 STUDY DESIGN

TREATMENT PHASE

This study will employ an open label nonrandomized design in the treatment of subjects with JDM. Study participation will consist of a screening visit and 5 protocol visits over six months (week 0, week 6, week 12, week 18, and week 24) for each subject, and phone follow-up in between in-person visits (week 2, week 4, week 8, week 10, week 14, week 16, week 20, and week 22). Some patients will undergo some of the screening tests at home, and present results at a screening visit. This will enable them to move to the week 0 visit simultaneously and begin treatment.

At Visit 1, which will be treatment initiation, eligible subjects will be instructed on the use and side effects of subcutaneous abatacept. Patients will be started on the study drug (abatacept) 125 mg SQ weekly for subjects with body weight \geq 50KG and 87.5 mg SQ for subjects with weight <50 KG. For patients not improving with therapy by at least 5% on

at least 3 of 6 core set measures (IMACS or PRINTO measures) at week 12, they would be offered the opportunity to increase their dose of treatment to abatacept 212.5 mg SQ weekly (125 mg prefilled syringe plus 87.5 mg prefilled syringe) for subjects with weight \geq 50KG and 137.5 mg SQ weekly (87.5 mg prefilled syringe plus 50 mg prefilled syringe) for subjects with weight <50KG, or to continue on their present dose.

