- Administer dose of study medication and observe after the injection for at least 15 minutes
- Schedule and instruct the subject to return for the next visit

Phone follow-up #3 (14 days (+/- 7 days after visit 2))

- Adverse events will be reviewed and recorded (NCI Common Toxicity criteria version 4.0).

Phone follow-up #4 (will occur 28 days (+/- 7 days) after visit 2.)

- Adverse event will be reviewed and recorded.

Visit 3 (week 12) will occur 42 days (+/- 10) days after Visit 2

- Review concomitant medication and query for adverse events and document in CRF.
- NCI Common Toxicity Assessment
- Obtain vital signs (HR,BP,RR, oral temperature and weight) and if indicated , by history of shortness of breath or lung disease, pulse oximetry)
- Medical history and perform a full physical examination
- Collect urine sample for pregnancy test for females of child bearing potential prior to administration of study medication (where applicable)
- Core set activity measures: physician global activity, patient/parent global activity, manual muscle testing (MMT-8), CMAS, HAQ/CHAQ, MDAAT, muscle enzymes, CHQ PF-50/SF- 36, and Disease activity score (DAS), physician global damage (VAS)
- Quality of life questionnaires: CHQ PF-50/SF- 36,DLQI , PROMIS/fatigue and Peds QL fatigue
- Physician and patient/parent assessment of study outcome
- Dermatology assessment performed by Rheumatologist : CDASI, photographs of skin rashes, periungual nailfold capillary assessment Dermatology Assessment Performed by Derm: CDASI, MD Global Skin Activity + Damage (Optional)

- Obtain blood samples for Chem-20, GGT, CK, aldolase, LDH, CBC with diff., von Willebrand Factor antigen level, Lymphocyte flow cytometry (TBNK cells) [**may be performed at home institution, up to 10 days before the visit date**]
- Urinalysis
- Collect research blood samples for Immunophenotyping (T, B cells and macrophages), gene expression and cytokine/chemokine analysis (see Section 3.1.h)
- Review if patient improved by $\geq 5\%$ in at least 3 of 6 core set measures (by IMACS or PRINTO measures). If patient did not meet this criterion and was rated by the study physician as unchanged or worsened since visit 1, an option to increase the dose to 212 mg (87.5 + 125 mg) SQ weekly for subjects with body weight ≥ 50 kg or to increase the dose to 137.5 mg (87.5 mg + 50 mg) for subjects with body weight < 50 kg will be presented.

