8.0 DOSE MODIFICATION

The dose of abatacept will remain constant until week 12. For patients not improving with therapy by at least 5% on at least 3 of 6 core set measures at week 12, they would be offered the opportunity to increase their dose of treatment to abatacept 212 mg (87.5 + 125 mg) for subjects with body weight \geq 50 kg or to abatacept 137.5 mg (87.5 mg+ 50 mg for subjects with body weight of < 50 kg) weekly subcutaneously, or to continue on their present dose.

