APPENDIX F ACTION PLAN FOR TREATMENT OF WORSENING OF DISEASE:

Criteria for disease worsening in a clinical trial, by which patients could be termed treatment failures and offered alternative therapies, were preliminarily defined at an IMACS Workshop. These criteria will be incorporated into this trial.

. In order to be classified as “worsening” in this trial subjects will have to meet the following criteria:

(1) Physician global worsening of ≥ 2 cm on the 10 cm visual analog scale (VAS) and a worsening of the manual muscle testing by $\geq 20\%$, or

(2) Global extra muscular organ disease activity (a composite of constitutional, cutaneous, skeletal, gastrointestinal, pulmonary and cardiac activity) worsening by ≥ 2 cm on a 10 cm VAS, or

(3) 3 of any 6 IMACS core set activity measures worse by $\geq 30\%$. And

(4) Subjects will have to meet the above criteria and be classified by the investigator as at least moderately clinically worse.

Patients who improve by less than 5% in at least 3 of 6 core set measures by week 12, will be considered to be not improved : These patients may be offered higher dose therapy at 212 mg (87.5 + 125 mg) for subjects with body weight ≥ 50 kg or 137.5 mg for subjects with body weight < 50 kg abatacept weekly.

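### The increased dose offered at week 12 to patients of 50 kg or more (212.5 mg weekly) exceeds the 200 mg weekly that the protocol gives as the highest dose tested in adults, and no visible text explains the excess

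*Combined protocol and SAP*

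**What the plan says.** - **Escalation, 50 kg or more.** Section 6.2 lets non-improvers at week 12 "increase their dose of treatment to abatacept 212.5 mg (125 mg prefilled syringe plus 87.5 mg prefilled syringe) weekly subcutaneously". Section 3.0 gives the same total: "abatacept 212.5 mg SQ weekly (125 mg prefilled syringe plus 87.5 mg prefilled syringe". The synopsis agrees, and Section 6.3 describes the second syringe.
- **Escalation, under 50 kg.** Section 6.2 offers an increase "to abatacept 137.5 mg (87.5 mg prefilled syringe plus 50 mg prefilled syringe) for subjects with body weight" below 50 kg.
- **The same total written differently.** Section 7.1 (Visit 3) has "an option to increase the dose to 212 mg (87.5 + 125 mg) SQ weekly", Section 8.0 has "increase their dose of treatment to abatacept 212 mg (87.5 + 125 mg", and Appendix F has "These patients may be offered higher dose therapy at 212 mg (87.5 + 125 mg".
- **Prior experience.** Within the risk/benefit text of Section 1.3.2, the paragraph on Study SC-1 (subcutaneous abatacept in adult RA) ends: "The highest dose tested in adults is 200 mg weekly".
- **Risk conclusion.** The same section later states: "The risks for those subjects involved in this study are reasonable when compared to the potential", and completes the comparison with the harm that the disease itself does.
- **Population.** Section 4.0 enrols from age 7 and from 25 kg, and includes adults with juvenile-onset disease. Age plays no part in the dose tier.

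**The concern.** A reader who sets Section 1.3.2 beside Section 6.2 finds a planned dose above the figure that the protocol gives as the highest tested in adults. The protocol neither remarks on this nor offers a reason. The offer extends to children of 50 kg or more. The paediatric safety data that are summarised come from a JIA programme that Section 1.3.1 labels as intravenous and for which Section 1.3.2 reports infusion reactions. No visible text gives safety data for any subcutaneous dose in children.

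Tolerance and safety form one of the two primary objectives (Section 2.1). Section 15 plans adverse event frequencies but does not say whether they will be split by dose. The enrolment pause in Section 9.0 (three or more patients with a related SAE) does not distinguish doses either. If some patients escalate, the planned outputs would not necessarily let a reader see what happened at the increased dose.

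**Working it through.** **Inputs.** Syringe strengths of 50, 87.5 and 125 mg (Section 6.0); increased doses (Section 6.2); stated adult maximum of 200 mg weekly (Section 1.3.2); weight limits of 25 and 50 kg (Sections 4.0 and 6.2); 10 patients and 24 weeks (Section 3.0).

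**1. The plan's own totals.** 125 + 87.5 = 212.5 mg and 87.5 + 50 = 137.5 mg. Section 6.2 is reproduced. The 212 mg in Sections 7.1 and 8.0 and in Appendix F is not the sum of the syringes printed beside it; the gap is 0.5/212.5 = 0.24%.

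**2. Against the stated maximum.**
- 50 kg or more: 212.5 − 200 = 12.5 mg, and 12.5/200 = 6.25% above. Read as 212 mg, 12/200 = 6.0% above, so the conclusion is unchanged.
- Under 50 kg: 137.5/200 = 0.69, so this tier is below 200 mg in absolute terms.

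**3. Per kilogram (dose divided by weight).** The documents give no adult weights, so the adult row rests on an assumed range of 50 to 100 kg.

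| Dose | Weight | mg/kg weekly |
|---|---|---|
| 137.5 mg (increased) | 25 kg | 5.5 |
| 137.5 mg (increased) | 49.9 kg | 2.76 |
| 212.5 mg (increased) | 50 kg | 4.25 |
| 87.5 mg (starting) | 25 kg | 3.5 |
| 200 mg (adult, assumed weight) | 50 to 100 kg | 4.0 to 2.0 |

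At the 25 kg entry minimum the increased dose is 5.5/4.0 = 1.4 to 5.5/2.0 = 2.75 times the adult figure, depending on the assumed adult weight. At 49.9 kg it lies inside the adult range. The starting dose at 25 kg (3.5 mg/kg) already exceeds 200 mg per kilogram in any adult heavier than 200/3.5 = 57 kg. The per-kilogram view therefore does not isolate escalation as the problem.

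**4. How much the trial could learn at the increased dose.** An escalated patient contributes 24 − 12 = 12 weeks in the main phase. The documents do not predict how many will escalate. If 1 to 3 of 10 do (an assumption), that is 12 to 36 of 10 × 24 = 240 patient-weeks, or 5% to 15%. With no SAE among 3 such patients, the exact two-sided 95% upper limit for the proportion is 1 − 0.025^(1/3) = 0.71. A table by dose can describe what happened but cannot establish tolerability.

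**The case against.** The strongest reply is that the excess is small, optional and monitored. It is 6.25%, offered only to patients who have not improved. Two-weekly adverse event contacts continue after week 12, and SAEs reach the DSMB within 24 hours. This stands, and it limits the weight of the point.

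A reader might draw stronger conclusions that the documents do not support:

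- **That the increased dose lies beyond all prior experience.** The route of the 200 mg figure is inferred from where the sentence sits. The risk section also relies on 1,955 intravenously treated adults and 190 children with JIA, and it calls subcutaneous safety consistent with the intravenous studies. No intravenous dose is stated, so exposures cannot be compared.
- **That nothing anywhere covers the dose.** The protocol refers to the Investigator's brochure for detail. The contents also list a subsection on pilot data in myositis that was not available to this review. Only the visible text can be called silent.
- **That patients or the DSMB would be misinformed.** The consent form was not available, and the DSMB reviews a protocol that prints both figures.
- **That the risk conclusion is contradicted.** It weighs risk against harm from the disease and makes no claim about dose. Its gap is that it does not mention escalation.
- **That small children are offered more than the adult maximum.** Patients under 50 kg are offered 137.5 mg, which is below 200 mg. The per-kilogram comparison depends on adult weights that the documents do not give.
- **That 212 against 212.5 mg is a dosing conflict.** Dosing is by whole prefilled syringes, so the difference is clerical.

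None of this removes the conflict between 200 mg and 212.5 mg, which stands in current text and goes unremarked.

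**Conclusion.** The concern holds in a limited form. For patients of 50 kg or more, adults or children, the protocol offers a weekly dose 12.5 mg (6.25%) above the one that it states as the highest tested in adults. No visible passage acknowledges or justifies this, and no visible text gives subcutaneous safety data in children. The comparison uses two figures printed in the protocol and rests on one reading: that the 200 mg statement concerns subcutaneous dosing, as its position implies.

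This is a should-fix point of disclosure and reconciliation. It is not a demonstration that the dose is unsafe or unprecedented. If supporting data exist, citing them resolves it. No view is taken on which dose is right.

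**What to change.** 1. Reconcile the escalation text (synopsis, Sections 3.0, 6.2, 6.3, 7.1 Visit 3 and 8.0, and Appendix F) with the 200 mg statement in Section 1.3.2. Either cite there the data that cover the increased doses, or amend the passages so that they no longer conflict.
2. Until that is done, state in the risk/benefit section, and point out to the DSMB, that the increased dose for patients of 50 kg or more exceeds the highest dose that the protocol says was tested in adults.
3. In Section 15, add a table of adverse events and SAEs by the dose being taken at onset (starting or increased), with patient-weeks on each. Label it descriptive only.
4. In the same amendment, make the stated total match its component syringes throughout.

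The cost is one wording amendment with its ethics approval and one extra table. The data for the table are already collected: Section 10.0 puts drug intake in a CRF medication log, and Section 3.2 has adverse events reviewed at visits and calls. The downside is a less favourable risk statement.

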6.3 Drug Ordering and Accountability

Initial Orders: The BMS project manager will be contacted for study drug requirements.

Re-Supply: The BMS project manager will be contacted for study drug requirements.

Packaging and Labeling: Abatacept SC is supplied in a box of 4 syringes.

Handling and Dispensing:

Administration of Study Medication

The investigational product will be stored in a secure area according to local regulations. The investigator is responsible for ensuring that it is dispensed only to study subjects and only by authorized personnel, as dictated by local regulations.

The investigator is responsible for ensuring that the investigational product is stored under the appropriate environmental conditions (temperature, light, and humidity), as described below:

Abatacept SC formulations (prefilled syringes) will be stored under refrigeration (approximately 2 to 8°C) and protected from long-term (more than 24 hours) exposure to light.

Abatacept injection, 125 mg/syringe (125 mg/mL) is ready to use solutions provided in pre-filled siliconized syringes with a 29 gauge needle.

Abatacept injection, 50 mg/syringe (50 mg/ml) and Abatacept injection, 87.5 mg/syringe (87.5 mg/ml) will also be available for subjects with body weight <50 kg

Care will be taken when handling the injectable drug products that are used in this protocol. Proper aseptic techniques will be used

Patients will be instructed to inject the full amount in the syringe (1 mL), which provides either 125 mg of Abatacept or 87.5 mg. At week 12 and weekly until the end of the study, some patients (those without improvement by at least 5% who are rated as unchanged or worsened by the study physician and those who agreed to this dose change) will be instructed to inject the full amount of a second syringe (1 ML) containing 87.5 mg of abatacept for subjects with body weight \geq 50 kg or a second syringe containing 50 mg of abatacept for subjects with body weight < 50 kg.

Abatacept injection should be inspected visually for particulate matter and discoloration prior to administration, whenever solution and container permit. ABATACEPT prefilled syringes should not be used if exhibiting particulate matter or discoloration. ABATACEPT should be clear and colorless to pale yellow, according to the directions provided in the Instructions for Use.

Injection sites (abdomen, thigh, upper arms) should be rotated and injections should never be given into areas where the skin is tender, bruised, red, or hard.

